5.1.1. Cohort A Treatment Assignment

There will be treatment assignment stratification by TTR genotype (variant or wild-type) only for Cohort A.

At enrollment, subjects in Cohort A were assigned to blinded active treatment in this study; tafamidis meglumine 20 mg or 80 mg once daily, in addition to standard of care (eg, diuretics) for up to 60 months based on the following:

- Subjects receiving tafamidis meglumine 20 mg or 80 mg in Study B3461028 continue the same blinded treatment assignment.
- Subjects assigned to placebo in Study B3461028 will be randomized (1:2) to blinded tafamidis meglumine 20 mg or 80 mg. Subjects assigned to placebo in Study B3461028 and randomized to tafamidis meglumine 80 mg will be permitted one blinded dose-reduction to 20 mg for adverse events related to tolerability.

Subjects in Cohort A will be assigned to open label treatment after protocol amendment 3.

Subjects receiving tafamidis meglumine 20 mg or 80 mg will be assigned to tafamidis 61 mg, once daily, in addition to standard of care (eg, diuretics), for up to 60 months. Subjects will be assigned to tafamidis meglumine 80 mg in regions where 61 mg tafamidis is unavailable.

Figure 3. Study Treatments

¹One permanent dose reduction to 20 mg talamidis meglumine is permitted for adverse events related to tolerability: Subjects will be assigned to 80 mg tafamidis meglumine in regions where 61 mg tafamidis is unavailable

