5.5.1. Dose-reduction

A one-time dose reduction to 20 mg tafamidis meglumine will be permitted for subjects after switching to 61 mg tafamidis.

Cohort A blinded dose reduction

In the event that subjects experience adverse events that may be associated with the tolerability of treatment with tafamidis that may impact dosing adherence, they should return to the clinic with their medication. If the investigator assesses that the tolerability issue is persistent and anticipated to impact dosing adherence and that the subject's safety is not compromised by continuing treatment, then the subject may request blinded treatment re-assignment to a lower dose. Only subjects assigned to 80 mg tafamidis in B3461045 after 30 months of placebo in Study B3461028 will be permitted one blinded dose-reduction to 20 mg.

The site personnel will enter the subject's study-specific identification (SSID) number into the IRT system and request blinded dose-reduction. The IRT system will provide a new container number for blinded treatment re-assignment for this subject.

If the subject was receiving the 80 mg dose in Study B3461045 after 30 months of placebo in Study B3461028, then the re-assignment will be to 20 mg. All other subjects will be maintained on the previously assigned dose but will still receive a new container number in order to maintain the blind.

If tolerability issues continue after the blinded re-assignment, the investigator has the option to discontinue dosing for this subject and to terminate study participation. In the event of early study discontinuation, the site staff will follow-up on the subject's vital status/transplant status 60 months after randomization into B3461045.

Cohort A & B open label dose reduction

In the event that subjects experience adverse events that may be associated with the tolerability of treatment with tafamidis that may impact dosing adherence, they should return to the clinic with their medication. If the investigator assesses that the tolerability issue is persistent and anticipated to impact dosing adherence and that the subject's safety is not

compromised by continuing treatment, then the subject may request treatment re-assignment to a lower dose. All subjects will be permitted one open label dose-reduction to 20 mg.

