# 6.5.1. Adverse Events

All AE data collected on the CRF will be presented in summary tables and data listings.

All adverse events that are observed from the time of first dosing with study medication until the treatment end date will be included in the safety analysis. Adverse events that occurred during treatment will be reported separately if the event occurred prior to randomization.

The effective duration of treatment is determined by the lag time. Any event occurring within the lag time, whether this occurs during a break in treatment or at the end of treatment, is attributed to the corresponding treatment period. A lag of 28 days will be used for this study. Treatment emergence is defined in Section 3.5.1.

All adverse events will be coded according to the Medical Dictionary for Regulatory Activities (MedDRA) and will be summarized by treatment group. The incidence of treatment-emergent adverse events will be tabulated by treatment group and by system organ class. The incidence of treatment-emergent adverse events will be displayed by severity and attribution. In addition, the incidence of serious adverse events and adverse events that cause withdrawal will be tabulated. All adverse events will be listed. All subjects in both Cohort A and B will be permitted one open label dose-reduction to 20 mg. All adverse events that led to temporary dose discontinuation or dose reduction will be summarized.

For Cohort A subjects who ended participation in B3461045 study without achieving the completion criteria of sustainable access to tafamidis by prescription, and allowed to return to the study and continue participation until they reach protocol defined study completion, adverse events that occurred between the time a subject ended the participation and subsequently returned will be collected and evaluated for treatment-emergence in the same manner as adverse events that occurred during the study participation.

Given that in B3461045 all subjects will be receiving active treatment, 3-tier analysis will not be performed on the adverse events.

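### SAP 6.5.1 does not separate real blinded dose reductions in Cohort A from masked re-assignments at an unchanged dose, so its dose-reduction summary may count both

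*SAP*

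**What the plan says.** SAP 6.5.1 plans the summary in one sentence: "All adverse events that led to temporary dose discontinuation or dose reduction will be summarized". The sentence before it concerns the open-label phase: "All subjects in both Cohort A and B will be permitted one open label dose-reduction to 20 mg". The section takes its adverse event data from the CRF, covers events from first dose to the end of treatment, and summarises by treatment group. For Cohort A, SAP 5.2 defines those groups as tafamidis/tafamidis and placebo/tafamidis, each pooling 20 mg and 80 mg.

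Protocol 5.5.1 describes the blinded procedure. For a persistent tolerability problem, the site enters the subject in the IRT to "request blinded dose-reduction. The IRT system will provide a new container number for blinded treatment re-assignment for this subject". Eligibility for a real change is narrow: "Only subjects assigned to 80 mg tafamidis in B3461045 after 30 months of placebo in Study B3461028 will be permitted one blinded dose-reduction". For the rest: "All other subjects will be maintained on the previously assigned dose but will still receive a new container number".

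Protocol 5.1.1 fixes who falls where. For parent-study placebo subjects: "Subjects assigned to placebo in Study B3461028 will be randomized (1:2) to blinded tafamidis meglumine 20 mg or 80 mg". For the others: "Subjects receiving tafamidis meglumine 20 mg or 80 mg in Study B3461028 continue the same blinded treatment assignment". Protocol 5.2 keeps subject and investigator blinded to dose until open-label assignment.

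**The concern.** A single request at the site had two possible outcomes that the site could not tell apart. If the CRF records the request as a reduction, the entry reads the same whether or not the dose fell. SAP 6.5.1 names no other data source, never mentions the masked procedure, and does not check the dose supplied. A programmer working from the SAP alone would not know that masked re-assignments exist.

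At stake is one tolerability summary in a study with long-term safety as a primary objective. Any miscounting would differ between the two displayed groups, because the share of requests that could lower the dose differs by group. Pooling 20 mg and 80 mg would hide this from a reader of the table.

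**Working it through.** The plan states no count or percentage of dose reductions, so there is no figure to reproduce. The check sets out who could be reduced, then the arithmetic that follows.

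**Step 1. Outcome of a blinded request (Protocol 5.1.1 and 5.5.1)**

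| Parent treatment | Blinded extension dose | SAP group | Result of request |
|---|---|---|---|
| Tafamidis 20 mg | 20 mg | tafamidis/tafamidis | dose unchanged |
| Tafamidis 80 mg | 80 mg | tafamidis/tafamidis | dose unchanged |
| Placebo | 20 mg | placebo/tafamidis | dose unchanged |
| Placebo | 80 mg | placebo/tafamidis | reduced to 20 mg |

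**Step 2. Tafamidis/tafamidis.** Neither row allows a real blinded reduction. The true number through this procedure is 0 by design, whatever the request rate.

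**Step 3. Placebo/tafamidis.** The 1:2 allocation puts 1/3 on 20 mg and 2/3 on 80 mg. Let k be the request rate of placebo-to-80 mg subjects relative to all other subjects (not in the documents; assumed).

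Masked share of requests = (1/3) / (1/3 + 2k/3) = 1/(1 + 2k)

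- k = 1: 1/3 = 33.3%
- k = 2: 1/5 = 20.0%
- k = 3: 1/7 = 14.3%

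**Step 4. Cohort A as a whole.** Let p be the share of Cohort A from parent placebo (not in the documents; assumed). The share eligible for a real reduction is f = 2p/3.

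Masked share of all blinded requests = (1 − f) / [(1 − f) + k·f]

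Example: p = 1/3 gives f = 0.222. At k = 2 the share is 0.778 / (0.778 + 0.444) = 63.6%.

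| p | f | k = 1 | k = 2 | k = 3 | k = 5 | k at which the share is 50% |
|---|---|---|---|---|---|---|
| 0.25 | 16.7% | 83.3% | 71.4% | 62.5% | 50.0% | 5.00 |
| 1/3 | 22.2% | 77.8% | 63.6% | 53.8% | 41.2% | 3.50 |
| 0.40 | 26.7% | 73.3% | 57.9% | 47.8% | 35.5% | 2.75 |
| 0.50 | 33.3% | 66.7% | 50.0% | 40.0% | 28.6% | 2.00 |

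The last column is (1 − f)/f. For any p below 0.75, most Cohort A subjects would have been re-supplied at the same dose had they asked. Whether most requests actually made were masked depends on p and k, and the documents give neither.

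**Step 5. What each way of counting would show.** Assume, for illustration, a blinded request rate of 10% in every subgroup.

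- Requests: 10% in tafamidis/tafamidis and 10% in placebo/tafamidis.
- Actual blinded reductions: 0% and 10% × 2/3 = 6.7%.

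These are blinded-period components only. The planned summary would also contain open-label reductions, which are real and available to everyone, so neither pair is the figure the table would print.

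**The case against.** A reader might infer that most blinded reductions were masked, and that the table will therefore report reductions that never happened. The documents support neither statement. They contain no request counts, and a masked majority fails once k passes 2.00 to 5.00 for the placebo shares above. Unequal rates are plausible: placebo-to-80 mg subjects were newly exposed, whereas tafamidis/tafamidis subjects had completed 30 months of treatment. The CRF is not in the documents either, so it is an inference that a blinded site would enter a masked request as a reduction. By the final analysis Cohort A is open label, and nothing prevents the use of actual dose. The supported wording is that masked re-assignments may be counted.

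The planned sentence also follows one about open-label reductions, so it could be read as meaning only those. That reading is possible but not stated. The section covers events from first dose, which takes in the blinded period, and sets no limit by phase.

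The most substantive objection concerns the remedy. Counting only actual reductions would create an artefact of its own. In step 5 tolerability is identical in the two groups, yet actual reductions show 0% against 6.7%, purely because of who was eligible. An adverse event that prompts a blinded request is itself a legitimate tolerability measure. This stands, and it is why the rows should be shown separately and not collapsed into a single count.

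Finally, the summary is descriptive. SAP 5.1 limits hypothesis testing to mortality and KCCQ, and no analysis of response to a lowered dose is planned. That limits the consequence but does not remove the ambiguity.

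**Conclusion.** The gap is real and narrow. SAP 6.5.1 has no rule to separate real from masked reductions in Cohort A's blinded period, and a blinded CRF entry alone cannot separate them. One result needs no assumption about rates: any blinded-period reduction attributed to this procedure in tafamidis/tafamidis would be false. In placebo/tafamidis the false part would be one third of requests at equal request rates, and less if placebo-to-80 mg subjects asked more often. Both statements apply only if the summary is built from the CRF request and not from the dose supplied. The number of events affected cannot be determined from the documents.

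Open-label reductions, Cohort B, mortality and overall treatment-emergent adverse event incidence are not affected. The point is worth acting on because it is cheap to settle and touches a safety readout. It does not threaten the study's main conclusions.

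**What to change.** In SAP 6.5.1, classify each adverse event recorded as leading to dose reduction by the IRT record of the dose dispensed before and after the request. Show three labelled rows by treatment group:

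- (a) blinded request with actual reduction;
- (b) blinded request with dose unchanged;
- (c) open-label reduction to 20 mg.

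Add a footnote that only placebo-to-80 mg subjects were eligible for (a). Row (a) alone should therefore not be compared between groups as a tolerability measure; (a) + (b) gives the blinded request rate. Use the dispensed dose in the SAP 6.4 exposure summary as well, so that the two outputs agree.

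The cost is about one SAP sentence plus the footnote, and a merge with IRT data the study already holds. No event is dropped and no clinical rule changes.

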#### 6.5.2. Laboratory Data

All clinical laboratory data (serum chemistry, coagulation, hematology, and urinalysis) will be subjected to clinical review and summarized by frequency of events and mean changes from baseline.

There was a Quality Event investigation (PR 2163545) concerning repeated data for the assessment of respiratory rate and urine dipstick at site 1121. The investigation could not confirm whether the repeated data was fraudulent or due to human error. To evaluate the impact of these findings on the overall interpretation of the endpoints potentially impacted, the laboratory analyses specified above will be repeated by excluding all subject data from this site 1121. Overall results will be compared to summaries generated by excluding the site to assess if there was a meaningful impact on the clinical interpretation.

# 6.5.3. Electrocardiogram

ECG values at each visit and change from baseline will be presented in summary tables and data listings. Descriptive statistics will be provided for each test result by visit.

Centrally over-read ECG variables will be summarized by mean change from baseline to end of study for heart rate, PR interval, QRS width, QT interval, and QTcB (Bazett's correction) and QTcF (Fridericia's correction) values. Additionally, the incidence of categorical increases in QTc intervals will be provided. Categories for QTcB and QTcF are  $\geq$ 450 msec,  $\geq$ 480 msec, and  $\geq$ 500 msec. Categories for QTcB and QTcF as change from baseline are:  $\geq$ 30 msec increase,  $\geq$ 60 msec increase, and  $\geq$ 75 msec increase. QTcF is considered the primary QTc value as this correction is anticipated to be more appropriate.

# 6.5.4. Physical Examinations and Vital Signs

*Physical examinations and vital signs (lying and standing blood pressure and pulse, respiratory rate, and temperature) will be summarized using descriptive statistics.* 

To assess the impact of the findings in the Quality Event investigation described in Section 6.5.2, vital signs summaries will also be generated by excluding all subject data from site 1121. Overall results of vital signs will be compared to summaries generated by excluding the site to assess if there was a meaningful impact on the clinical interpretation.

# 7. INTERIM ANALYSES

# 7.1. Introduction

Interim analyses may be performed if required to meet regulatory requirements and as requested by the Data Monitoring Committee. Interim analyses may also be performed during the course of the study to allow for the reporting of data to the scientific community.

# 7.2. Interim Analyses and Summaries

Interim analyses will include either all the analyses or a subset of the summaries described in Sections 5 and 6.

DMB02-GSOP-RF02 3.0 STATISTICAL ANALYSIS PLAN TEMPLATE 30-Jun-2015 PFIZER CONFIDENTIAL Page 17 TMF Doc ID: 98.03

#### 9. APPENDICES

#### **Appendix 1. SUMMARY OF ANALYSES**

#### **Summary of Proposed Analyses**

End Point or Assessment	Overall ##	Wild-type vs Variant
All cause mortality.#	Х	Х
Cardiovascular related mortality.#	Х	х
Frequency of all cause hospitalization.	х	X
Frequency of cardiovascular related hospitalization (including heart failure, arrhythmia, myocardial infarction, stroke and other cardiovascular related events).	x	X
Change from baseline at each visit in Kansas City Cardiomyopathy Questionnaire Overall Score, domain scores (Physical limitation, Symptom stability, Symptom frequency, Symptom burden, Total symptom, Self efficacy, Social limitation, and Quality of life) and clinical summary score #	X	х
New York Heart Association classification at each visit.	X	X
Change from baseline in Body Mass Index/modified Body Mass Index at each visit.	X	X
Change from baseline in NT-proBNP at each	х	х
Change from baseline in Troponin I at each visit.#	х	х
Assessment of physical examinations, use of concomitant medications, electrocardiograms (ECGs), clinical laboratory testing, vital signs at each visit.	X	x

# Cohort A Analysis will include data from B3461028.

## Overall implies that it is not subgroup analysis. For Cohort A, summaries are provided by

"Tafamidis/Tafamidis" and "Placebo/Tafamidis" groups. For Cohort B, summaries are provided by "Tafamidis" group.

#### Appendix 1.1. Definition and Use of Visit Windows in Reporting

For the purpose of this study, Day 1 is defined as the first dose day under this protocol (except for mortality-based endpoints, KCCQ, NT-proBNP, and Troponin I).

The following describes the clinical visit windows allowed within the protocol:

Clinic Visits (Months 6, 12, 18, 24, 30, 36, 42, 48, 54) ±2 weeks

End of Study Visit (Month 60) ±2 weeks or Early Study Discontinuation

However, in order to maximize the use of all available data, the visit windows for each visit are expanded as follows:

Clinic Visits (Months 6, 12, 18, 24, 30, 36, 42, 48, 54) ±3 months

All nominal visits (months 6, 12, 18, 24, 30, 36, 42, 48, 54) will use the data as collected from that visit. Early termination visits will never replace an existing visit. If the visit covered by the windowing rules above is already populated with an existing nominal visit, then the early termination visit should be mapped forward to the next 6 month visit.

Data from endpoints that are collected at "Month 3" either in France or Germany as part of the country-specific protocol amendment will be summarized descriptively as 'Month 3- Unscheduled' and will not be subject to the windowing rules described above.

Analyses of KCCQ, NT-proBNP, Troponin I will combine data from B3461028 study. For these endpoints, visits for B3461045 will be evaluated as "30 Months" plus the visit window calculated using the B3461045 windowing rules specified above.

#### **Appendix 2. STATISTICAL METHODOLOGY DETAILS**

Sample SAS code for time to event analysis is given below.

PROC LIFETEST DATA=xxx PLOTS=(s) graphics; TIME dur \*status(0); STRATA trt; RUN;

PROC PHREG DATA=xxx; MODEL dur\*status(0)=trt genotype NYHAbase/ ties=EXACT; RUN;

Sample SAS code to fit the mixed model repeated measures is given below. The response variable Y is the change from baseline at the study visits.

PROC MIXED DATA=xxx METHOD=REML EMPIRICAL; CLASS pid center trt visit genotype; MODEL y= ybase trt visit genotype trt \*visit; RANDOM int/SUBJECT=center; REPEATED visit /SUBJECT= pid (center) r type=UN; RUN;

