# 5.1. Hypotheses and Decision Rules

The primary objective of the study is to obtain additional, long term, safety data for tafamidis in subjects with transthyretin cardiomyopathy (ATTR-CM) and to provide investigational product, tafamidis, to ATTR-CM subjects who complete 30 months of blinded treatment on protocol B3461028 (Cohort A) and to Subjects diagnosed with ATTR-CM who have not previously participated in Study B3461028 (Cohort B). Therefore, only limited hypothesis testing ie, mortality and change from baseline in KCCQ for Cohort A subjects will be performed. All hypothesis testing will be conducted using two-sided tests with alpha = 0.05 level of significance. Since the primary objective of the study is to collect safety information, no multiplicity adjustment will be done. No hypothesis testing will be done on Cohort B subjects.

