# 6.2.3. Kansas City Cardiomyopathy Questionnaire

The KCCQ will be summarized by the following summary scores calculated using the guidelines established in the KCCQ scoring instructions from the developer:

Physical limitations	Self-efficacy
Symptom stability	Quality of life
Symptom frequency	Social limitation
Symptom burden	Overall summary score
Total symptom score	Clinical summary score

For Cohort A, the overall, domain, and clinical summary scores will be evaluated as a change from baseline at each visit using a MMRM (repeated measures mixed model) with an unstructured covariance matrix (or as appropriate) with center and subject-within-center as a random effects and treatment (tafamidis/tafamidis and placebo/tafamidis), visit, TTR genotype (variant and wild- type), and visit-by-treatment interaction, as fixed effects and baseline score as covariate. *Data will also be summarized by each scheduled assessment*.

As defined in Section 3.4, the baseline for Study B3461028 will be used as the baseline for all KCCQ based analyses. All visits from Study B3461028 will also be included in the repeated measures model described above.

For Cohort B, descriptive statistics for change from baseline at each post-baseline visit will be provided.

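### The KCCQ mixed-model code uses a centre-clustered sandwich variance with no small-sample correction, so the visit-wise 5% tests reject too often

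*SAP*

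**What the plan says.** SAP 6.2.3 evaluates change from baseline in ten KCCQ scores at each visit, for Cohort A, with an "MMRM (repeated measures mixed model) with an unstructured covariance matrix (or as appropriate"). The fixed effects are treatment, visit, genotype, visit-by-treatment and baseline score. The random effects are described as "with center and subject-within-center as a random effects". All parent-study visits enter the model, and SAP Appendix 1.1 places extension visits at 30 months plus the extension visit time.

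The section names no variance estimator, clustering level or degrees-of-freedom method. These appear only through the sample code in SAP Appendix 2, which opens with "PROC MIXED DATA=xxx METHOD=REML EMPIRICAL; CLASS pid center trt visit genotype" and continues, after the model statement, with "RANDOM int/SUBJECT=center; REPEATED visit /SUBJECT= pid (center) r type=UN". There is no `DDFM=` option.

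SAP 5.1 limits formal testing to mortality and KCCQ in Cohort A. It adds: "All hypothesis testing will be conducted using two-sided tests with alpha = 0.05 level of significance", and "no multiplicity adjustment will be done".

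**The concern.** `EMPIRICAL` replaces the model-based variance of the fixed effects with a sandwich estimate summed over independent blocks. Subjects are nested in centre and centre is the subject of the `RANDOM` statement, so those blocks are centres, not patients. This is a reading of how the software works; the SAP does not say it.

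An uncorrected sandwich is biased downwards and variable when clusters are few or unequal. The default degrees of freedom do not reflect the number of centres. Both faults make p-values too small and intervals too narrow.

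KCCQ is one of only two outcomes that are formally tested. Thin late visits are foreseeable. Subjects leave when tafamidis becomes available by prescription (Protocol Section 3), and it was already approved for ATTR-CM in the United States and Japan (Protocol 1.1). SAP 6.3 also repeats every analysis within wild-type and variant subjects, which shrinks the data further.

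**Working it through.** **Benchmark.** The documents give no sample size or power for this analysis, so there is no figure to reproduce. The only benchmark is the nominal 5%.

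**Inputs from the documents.**
- At most 441 subjects, the parent-study total (Protocol 1.2).
- Ten extension assessments, Months 6 to 60.
- Fixed effects and code as described above.

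**Assumptions not in the documents.**
- 15 to 100 centres of unequal size (coefficient of variation 1).
- 2:1 pooled tafamidis to placebo.
- Five 6-monthly parent visits.
- 10% or 30% of subjects still observed at Month 90.
- SD 20.

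Five parent plus ten extension visits make 15, so the unstructured matrix has 15 × 16 / 2 = 120 parameters.

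**Run 1: known covariance.** Centre ICC 0.05, 9,600 null replicates per scenario, Monte Carlo SE √(0.05 × 0.95 / 9600) = 0.22 points. Type I error (%) of the code as written:

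| Centres | M30, 10% retention | M90, 10% | M30, 30% retention | M90, 30% |
|---|---|---|---|---|
| 15 | 10.1 | 11.6 | 10.4 | 11.4 |
| 30 | 7.6 | 8.8 | 8.0 | 8.0 |
| 48 | 6.3 | 7.8 | 6.8 | 7.3 |
| 60 | 6.3 | 7.6 | 6.6 | 6.4 |
| 100 | 5.9 | 6.9 | 6.2 | 6.3 |

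The model-based test with the true covariance gave 4.6-5.3%, so the set-up is calibrated.

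A simpler single-visit simulation used 4,000 replicates, ICC 0.03 and 60-250 subjects observed. It gave 10.6-11.8% (15 centres), 8.1-8.9% (30) and 6.2-8.7% (45), with model-based errors at 4.4-5.2%.

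**Where the excess comes from.** Take 60 centres, Month 90, 10% retention (about 26 centres and 44 subjects left). The sandwich variance averages 0.925 of the true variance, so the standard error is about √0.925 = 0.962 of what it should be. That alone gives 2 × [1 − Φ(1.96 × 0.962)] = 5.9%. The rest of the 7.6% comes from referring a noisy variance to large degrees of freedom. Using t with (centres at the visit − 1) df lowers 7.6% to 6.3%. Adding a jackknife-type (CR3) correction gives 5.0%. Over all centre counts, the CR3-type correction with that t reference gave 4.8-6.0% at Months 30 and 90.

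**Run 2: unstructured matrix estimated.** Here the centre ICC was 0, no centre effect was fitted, and a normal reference was used. There were 378 to 959 replicates per scenario, and the Monte Carlo SE was 0.8-1.8 points. Type I error (%):

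| Centres, retention | Sandwich M30 | Sandwich M90 | Model-based, unadjusted, M90 |
|---|---|---|---|
| 30, 10% | 6.3 | 14.6 | 8.7 |
| 60, 10% | 6.0 | 10.8 | 6.9 |
| 30, 30% | 7.2 | 8.1 | 4.7 |
| 60, 30% | 6.1 | 6.7 | 5.7 |

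At sparse visits, part of the inflation therefore comes from estimating 120 covariance parameters. It remains when the sandwich is dropped without a small-sample adjustment.

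**Random effects, text against code.** The text adds a subject-within-centre intercept with variance s². With J the all-ones matrix and R unrestricted, s²J + R is again an unrestricted covariance matrix. The text and the code therefore give the same marginal model, and s² is not separately identifiable.

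**The case against.** KCCQ is an 'other' endpoint in a mainly descriptive study, and no decision rule rests on it. The code is labelled as a sample and contains no statement for a visit contrast, so testing at each visit is inferred from SAP 5.1 and 6.2.3. With 441 parent-study subjects across several continents, many centres are plausible; at 60-100 centres with known covariance the excess is only about 1-3 points. A sandwich also protects against a wrong covariance model, and the SAP gives consistency with the parent-study model as one reason for including the centre effect. All of this stands and limits the severity. It does not remove the point: nothing else in the SAP specifies the standard errors, and the estimated error was above 5% in every scenario at every centre count tried.

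A reader might go further in three ways that the documents do not support.
- **Text and code contradict each other, and this causes the inflation.** They do not under an unstructured matrix, as the algebra shows. The wording is loose, but it is not the cause.
- **The problem is confined to late visits.** Month 30 is inflated too, and with 30% retention Month 90 was sometimes no worse (8.0% at both for 30 centres).
- **The single baseline slope over all visits is a related fault.** Nothing here shows that it affects the error rate; a baseline-by-visit term is a separate modelling preference.

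**Conclusion.** The concern holds for the variance estimator. As coded, the KCCQ tests do not keep their nominal 5%, and interval coverage falls short by the same amount; for example, a 7.6% error rate means 92.4% coverage.

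With known covariance the error is about 6-8% at 45-100 centres (one single-visit scenario at 45 centres reached 8.7%), 8-9% at 30 and 10-12% at 15. The least favourable results, 10.8% and 14.6% at Month 90, need 10% retention, an estimated unstructured matrix, and 60 and 30 centres respectively.

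No single figure can be attached to this trial, because the number of centres, their sizes, retention and the parent allocation ratio are all assumed. It would also be wrong to infer that deleting `EMPIRICAL` is enough: with no small-sample adjustment, 6.9-8.7% remained at Month 90 under 10% retention. The importance is modest because the endpoint is not primary.

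**What to change.** In SAP 6.2.3, state the variance estimator, the clustering level and the degrees-of-freedom method, and make Appendix 2 match. Two options are reasonable:
- **Model-based errors:** replace `EMPIRICAL` with model-based standard errors, `TYPE=UN` on subject and `DDFM=KR`. Kenward-Roger was not itself simulated here, so its performance at very sparse visits is expected rather than shown.
- **Robust errors:** keep a sandwich clustered by centre, with a bias correction and degrees of freedom based on the centres contributing at the visit. This is the option checked above, with known covariance only.

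Replace the open-ended allowance for another covariance with a fixed fallback order if the unstructured fit does not converge, for example heterogeneous Toeplitz and then AR(1), using the bias-corrected sandwich with any structured fallback. SAP 6.2 already anticipates convergence trouble when it keeps Month 3 data out of the models.

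As tidying only, delete the subject-within-centre term from 6.2.3. It is not identifiable under the unstructured matrix, and under a structured fallback it would make the text and code differ.

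The cost is SAP wording and code options, with no new data. Intervals become slightly wider. Choosing model-based errors also gives up the sandwich's protection against a misspecified covariance. If the parent study used the same sandwich, which these documents do not show, its KCCQ results would be less directly comparable.
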